STUDY EVALUATIONS: All subjects were evaluated using the Aberrant Behavior Checklist (ABC) Global Scale and 5 Subscales (Irritability/Agitation, Lethargy/Social Withdrawal; Stereotypic Behavior; Hyperactivity/ Noncompliance and Inappropriate Speech); and the Clinical Global Impressions Severity of Illness (CGI-S) and Improvement/Change (CGI-C) scales at baseline, week 2 (interim), week 4(endpoint) and week 8 (post-procedure) of the study. Test group subjects were additionally evaluated at 6 months post-procedure.

STUDY RESULTS

Primary Outcome Measure: Primary outcome measure was predefined as the mean change from baseline to endpoint in the Aberrant Behavior Checklist (ABC) Irritability & Agitation Subscale score. Primary efficacy study success was pre-established as the detection of a minimum mean difference of -8.5 points between test and placebo groups in the baseline to endpoint change in ABC Irritability Subscale score adjusted for baseline ABC Irritability Subscale score.

The adjusted mean difference in the baseline to study endpoint change in the ABC Irritability Subscale score between all 40 active procedure subjects and placebo subjects was -13.82 in favor of the active procedure group, notably greater than the preestablished study success criteria of a -8.5-point difference. ANCOVA analysis found this difference to be statistically significant at p<0.0001 (F=30.07), independent of baseline ABC Irritability Subscale score.

ABC	Combined (n=401)		Test (n=21)		Cross-Over (n=19)		Placebo	o (n=19)
Irritability	Mean	SD	Mean	SD	Mean	SD	Mean	SD
Baseline	30.45	6.74	30.52	6.73	30.37	6.94	29.58	6.83
Endpoint	16.90	9.05	15.71	9.94	18.21	8.02	29.89	6.55

Change -13.55 6.387	-14.81	6.40	-12.16	6.21	0.32	1.38
---------------------	--------	------	--------	------	------	------

The table below show the mean and standard deviation and the magnitude of change in ABC Irritability Subscale scores from baseline to endpoint.

Positive Responder Rate: *Positive Response Rate* was defined as satisfaction of both of the following 2 criteria:

- ≥ 25% reduction from baseline to endpoint in the ABC Irritability Subscale score;
 AND
- CGI-I scale rating of 1 (very much improved) or 2 (much improved) at study endpoint

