CONCLUSION: The Erchonia® HLS Laser is an effective tool for improving irritability and the presentation of other symptoms and behaviors associated with autistic disorder in children and adolescents, with positive changes maintained and augmented over time, including a six-month follow-up period during which time no procedure administration occurred.

STUDY RATIONALE

Considering the positive outcomes of the prior feasibility and clinical studies, it is determined that application of the Erchonia® HLS may provide a simple, non-invasive, safe, effective and side-effect free alternative therapy to reduce the severity of irritability symptoms and behaviors of autistic disorder in children. The currently proposed full-scale controlled pivotal trial is intended to demonstrate this to a statistically significant and clinically meaningful extent.

STUDY DESIGN

This clinical study is a double-blind, placebo-controlled randomized parallel group design.

TREATMENT GROUPS

Each subject is randomized to the test treatment group or to the placebo treatment group, as follows:

- ➤ Test Group: Subjects randomized to the test group will receive the study treatments with the active (true) Erchonia® HLS device.
- ➤ Placebo Group: Subjects randomized to the placebo group will receive the study treatments with the 'fake' (placebo) Erchonia® HLS device.

DOUBLE BLIND DESIGN

This clinical study will be a double-blind design, such that neither the subject nor the investigator will be aware of whether a subject has been assigned to the test group or to the control group until after the study is complete.

Maintenance of study double-blind throughout the study duration will be achieved as follows:

- 1) Each subject will be randomly assigned to Treatment Group A or to Treatment Group B. Subjects assigned to Treatment Group A will be treated with the Erchonia® HLS A and subjects assigned to Treatment Group B will be treated with Erchonia® HLS B. Only the study Sponsor will know which label ('A' or 'B') corresponds to the actual (test) HLS device and which label corresponds to the 'fake' device until the final study data analysis is complete. The Sponsor will ensure that this information is stored and maintained confidentially at the Sponsor's work site. This knowledge will not be shared with the investigators, the subjects, or the study Monitor until the final data analysis is complete.

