- 5. An individual for whom the caregiver decides not to permit participation in the study will continue to work with the physician on the ASD treatment plan goals for the minor patient.

Compensation

A subject or his or her caregiver(s) will not be offered money or any other form of compensation to participate in the clinical study; however, there will also not be any charge for the cost of the study treatments with the Erchonia® HLS laser device or for the cost of any other directly-related evaluations or measurements that occur as part of the subject's participation in this study.

Subject Sample Size

There will be 40 qualified subjects enrolled in this clinical study:

- 20 subjects in the test group
- 20 subjects in the control (placebo) group

Rationale and Justification for Sample Size

This study is powered to compare one active arm with placebo. Sample size calculation is based on the primary efficacy measure of the mean change from study baseline to endpoint (end of the 4-week treatment period) in the Aberrant Behavior Checklist (ABC) Irritability Subscale score adjusted for the baseline ABC Irritability Subscale score.

Based on detecting a mean difference of -8.5 points between test and placebo groups in the change in ABC Irritability Subscale score adjusted for the baseline ABC Irritability Subscale score being considered clinically relevant with a SD of 8.9, a two-sided test with 80% power and a 5% level of significance, the number of subjects needed per treatment group is 18.

From here, it is anticipated that about one-tenth of subjects overall may withdraw or be terminated from the study prior to completion for various reasons. Therefore, the following formula is used to determine the final needed starting sample size for each procedure arm:

Final sample size = sample size X 1/(1-d); where d = # expected dropouts/# subjects enrolled.

Final sample size = $18 \times 1/(1-0.11)$; where d = 2/19

Final sample size = 18 X 1/0.89 = 18 X 1.124 = 20 subjects per treatment group.

Therefore, a minimum starting sample size of 20 subjects in each treatment group (40 subjects in total) is needed to insure that a sufficient number remains at study endpoint (18 evaluable subjects per treatment group) for any significant differences found between treatment groups to be considered statistically valid and representative of the general population being sampled.

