Following completion of the 4-week Treatment Administration Phase (after completion of all 8 treatment administrations), the following study measures will be recorded:

- Aberrant Behavior Checklist (ABC)
- Clinical Global Impressions (CGI)
- Caregiver Satisfaction with Study Outcome
- Caregiver Perceived Group Allocation and Rationale
- > Administration Investigator Perceived Group Allocation and Rationale

POST-TREATMENT EVALUATION PHASE

WEEK 8: All Subjects

Four weeks following completion of the 4-week Treatment Administration Phase (8 weeks after study onset), the following study measures will be recorded:

- ➤ Aberrant Behavior Checklist (ABC)
- Clinical Global Impressions (CGI)
- Medication and therapy use review
- > Adverse events evaluation
- > Caregiver Satisfaction with Study Outcome
- Caregiver Perceived Group Allocation and Rationale
- Administration Investigator Perceived Group Allocation and Rationale

STATISTICAL ANALYSIS PLAN

The aim of this study is to determine if the treatment effect of the Erchonia® HLS laser device for the active treatment group is greater than that for the placebo treatment group.

The study will be considered a success if, using the Intent-To-Treat (ITT) Last Observation Carried Forward (LOCF) analysis, the primary endpoint is statistically significant at the 0.05 level.

PRIMARY EFFICACY OUTCOME MEASURE

The primary efficacy outcome measure in this study is the mean change from baseline to study endpoint (end of the four-week treatment period) in the Aberrant Behavior Checklist (ABC) Irritability Subscale score.

Study success will be established through the detection of a minimum mean difference of -8.5 points between test and placebo groups in the change in ABC Irritability Subscale score from baseline to study endpoint (end of treatment week 4) adjusted for the baseline ABC Irritability Subscale score. The -8.5-point mean difference between treatment groups is considered clinically relevant with a SD of 8.9, a two-sided test with 80% power and a 5% level of significance.

Null Hypothesis: There is no difference in the mean change in ABC Irritability Subscale score from baseline to study endpoint adjusted for the baseline ABC Irritability Subscale score between active treatment and placebo groups, to the effect of less than -8.5 points.

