Alternative Hypothesis: There is a difference in the mean change in ABC Irritability Subscale score from baseline to study endpoint adjusted for the baseline ABC Irritability Subscale score between active treatment and placebo groups, to the effect of -8.5 points or greater.

Rationale for Primary Efficacy Outcome Measure

Determination, application and support of the detection of a mean difference of -8.5 points between test and placebo groups in the change in the ABC Irritability Subscale score from Baseline to study Endpoint adjusted for the baseline ABC Irritability Subscale score being considered clinically relevant is based on the results of the clinical study for Abilify® (aripiprazole) that resulted in FDA clearance of the drug for the same exact intended indication as in this proposed pivotal trial combined with the results of a feasibility study employing the Erchonia® HLS Laser Device with the same device output parameters and treatment administration protocol as proposed for the current pivotal study.

Abilify® (apriprazole) Study: In the Abilify® study, the primary efficacy endpoint was the mean change from Baseline to Week 8 LOCF in the ABC Irritability Subscale score. There was a statistically significant difference between the treatment groups in favor of Abilify® (aripiprazole) in the adjusted mean change from Baseline to Week 8 LOCF (study Endpoint) in the ABC Irritability Subscale score of -7.9 (placebo -5.0, aripiprazole -12.9, difference -7.9, 95% CI (-11.7, -4.1), p<0.001). It was concluded that this change demonstrated clinically relevant and statistically significant improvement compared with placebo on the primary efficacy endpoint in the adjusted mean change from Baseline on the ABC Irritability Subscale at Endpoint.

FDA independent analysis concluded that the results of the clinical trials showed that treatment with aripiprazole is efficacious in improving the symptoms of irritability in children and adolescents with autism, as demonstrated by the results on the primary endpoint, ABC Irritability Subscale. It was stated that **aripiprazole showed clinically meaningful and statistically significant improvement compared with placebo** through study Endpoint evaluation on the primary efficacy measure of mean change from Baseline to Week 8 in the ABC Irritability Subscale score.

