For the continuous primary efficacy measure of ABC Irritability Subscale score, change scores will be evaluated by analysis of covariance (ANCOVA). The ANCOVA models for LOCF data sets will include the baseline measure as a covariate and treatment (active of placebo) as main effects.

Secondary Measures Analysis

- ➤ For the continuous secondary efficacy measures of the other 4 ABC Subscale scores, and the Global Score, change scores will be evaluated by analysis of covariance (ANCOVA). The ANCOVA models for LOCF data sets will include the baseline measure as a covariate and treatment (active of placebo) as main effects. A two-way significance level of 5% will be considered statistically significant.
- ➤ The categorical measures of the CGI will be analyzed within the framework of the generalized Cochran-Mantel Haenszel (CMH) procedure.
- Responder rate will be evaluated using Fisher's exact test to compare the proportion of responder rates between the test and control groups.

P-values will be 2-tailed tests of significance rounded to 3 decimal places. All analyses will be performed at the 5% significance level.

CAREGIVER SATISFACTION

Caregiver satisfaction ratings will be descriptively presented through the number and percentage of responses per response category. Fischer's Exact Test will be employed to determine the significance of the difference in categorical responses between treatment groups.

BLINDING EFFICACY EVALUATION

Blinding efficacy evaluation will be conducted through analysis of findings from the Caregiver and the Assessment Investigator Perceived Subject Group Allocation and Rationale responses, recorded at completion of the procedure administration phase (study endpoint).

Statistical evaluation of blinding efficacy will be performed as follows:

- (i) The percentage of caregivers who correctly perceived the subject's procedure group assignment and the percentage of caregivers who did not correctly perceive the subject's procedure group assignment will be calculated.
- (ii) The percentage of times the assessment investigators correctly perceived subjects' procedure group assignment and the percentage of times the assessment investigators did not correctly perceive subjects' procedure group assignment will be calculated.

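### The plan gives two success rules, p<0.05 and a difference of at least 8.5 points, without reconciling them; its 80% power belongs only to the first, and as a pass mark 8.5 is met about half the time when the true difference is 8.5

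*Combined protocol and SAP*

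**What the plan says.** The combined protocol and SAP states success twice, in adjacent sections.

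- Statistical Analysis Plan, opening: the study succeeds if, on the ITT/LOCF analysis, "the primary endpoint is statistically significant at the 0.05 level".
- Primary Efficacy Outcome Measure: "Study success will be established through the detection of a minimum mean difference of -8.5 points between test and placebo groups", on the change to week 4 with baseline adjustment.

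The hypotheses in the same section follow the second version. The null is qualified "between active treatment and placebo groups, to the effect of less than -8.5 points", and the alternative "to the effect of -8.5 points or greater".

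The Primary Efficacy Analysis contains no comparison with -8.5: "The ANCOVA models for LOCF data sets will include the baseline measure as a covariate and treatment (active of placebo) as main effects".

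The Rationale and Justification for Sample Size takes a difference of -8.5 and SD 8.9 and concludes: "a two-sided test with 80% power and a 5% level of significance, the number of subjects needed per treatment group is 18". Allowing for dropout, 20 per arm are enrolled.

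Two other places bear on how -8.5 is meant. Under Supportive Clinical Data, the previous sham-controlled trial's observed adjusted difference of -13.82 is called "notably greater than the preestablished study success criteria of a -8.5-point difference". The Study Rationale says that the present trial should show the benefit "to a statistically significant and clinically meaningful extent".

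**The concern.** A planning difference is the true effect at which a test of zero has the chosen power. It is not the value that the estimate must reach. Here the same -8.5 appears in both roles. An unbiased, symmetric estimate falls short of its own true value half the time, so a rule requiring the estimate to reach -8.5 cannot have 80% power at a true -8.5.

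Two things are at stake. First, results in a realistic range are undecided: the plan does not say whether a significant difference smaller than 8.5 points is a success. The plan's own benchmark falls in that range, since it cites an aripiprazole difference of -7.9 as clinically meaningful. Second, if -8.5 is binding, the stated power is wrong. The trial is meant to support a de novo application after an earlier denial, so its success rule should not be open to choice once the data are seen.

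**Working it through.** **Inputs.** Difference 8.5, SD 8.9, two-sided 5%, 80% power, 18 evaluable and 20 enrolled per arm (Rationale and Justification for Sample Size); 1:1 allocation (Treatment Group Randomization). Differences are given below as absolute values in favour of active.

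**1. The plan's own figure.** n = 2 × (1.960 + 0.842)² × 8.9² / 8.5² = 17.2, rounded up to 18 per arm. This is the formula for a test of zero difference, so the stated 18 is reproduced. Noncentral-t power at a true 8.5 is 79.5% with 18 per arm and 83.7% with 20.

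**2. Smallest significant difference.** SE = 8.9 × √(2/n) = 2.967 (n = 18) or 2.814 (n = 20). Multiplied by the 97.5% t quantile (2.032 or 2.024), this gives 6.03 or 5.70 points.

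**3. Pass mark of 8.5 on the estimate.** P(observed ≥ 8.5) = Φ((true − 8.5)/SE). At a true 8.5 this is Φ(0) = 50%, whatever n or SD.

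**4. Both conditions together.** With 18 per arm, an observed 8.5 is non-significant only if the residual SD exceeds 8.5 / (2.032 × √(2/18)) = 12.5. The chance of reaching 8.5 without significance is below 0.0001, so the joint rule also gives 50%. Simulation agrees: 50.1% at 18 per arm, 49.9% at 20, 50.0% at 100.

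**5. Significant but short of 8.5, at a true 8.5.** 79.5% − 50.0% = 29.5% (n = 18); 83.7% − 50.0% = 33.7% (n = 20).

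**6. True difference giving an 80% chance under the pass mark.** 8.5 + 0.842 × SE = 11.0 (n = 18) or 10.9 (n = 20).

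| At a true 8.5, SD 8.9 | 18 per arm | 20 per arm |
|---|---|---|
| p<0.05 against zero | 79.5% | 83.7% |
| Observed ≥ 8.5, alone or with p<0.05 | 50% | 50% |
| Significant but below 8.5 | 29.5% | 33.7% |
| True difference for 80% under the pass mark | 11.0 | 10.9 |

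**7. Other true effects, pass mark, 18 per arm, SD 8.9.** 42% at 7.9 (the cited aripiprazole difference); 58% at 9.09 (the feasibility study's change, which had no control group); 96% at 13.82 (the previous trial), where the zero-difference test has 99.5%.

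**8. Sensitivity to the SD.** The previous trial's pooled change SD is √((20 × 6.40² + 18 × 1.38²)/38) = 4.74. At SD 4.7 and 18 per arm, the smallest significant difference is 2.032 × 4.7/3 = 3.18, so the undecided range widens to about 3.2 to 8.5. The 50% does not move.

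**9. Literal reading of the hypotheses.** If the 95% CI had to lie wholly beyond 8.5, the chance at a true 8.5 would be 2.5% at any n. An 80% chance would need a true difference of 8.5 + 2.802 × SE = 16.8 (n = 18) or 16.4 (n = 20).

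**The case against.** The best defence is that -8.5 is only the planning difference, restated loosely. The opening statement is the only one that names an analysis set, a missing-data method and a significance level. The aim just before it is only superiority to placebo. The ANCOVA makes no comparison with -8.5, and the sentence after the -8.5 statement attaches the SD, power and alpha from the sample-size section. The previous trial was run under another protocol, so its use of -8.5 is indirect evidence. This reading is available, but it does not account for a sentence that defines study success by -8.5, or for hypotheses built on that number. The previous trial shows the sponsor applying the same criterion to an observed estimate.

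Other points stand as limits:

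- The 50% is a general property of such rules. It applies only if -8.5 is a pass mark and the true effect is -8.5.
- If the true effect is near -13.82, the rules rarely disagree. The 96% above pairs that effect with SD 8.9; with SD 4.74 it is 99.96%.
- The 4.74 pools very unequal arm SDs of raw change, and the plan does not say whether 8.9 is a raw or a residual SD. The -6.0 edge and the 29.5% depend on that.
- No reading inflates false positives. At zero effect (SD 8.9, 18 per arm), an estimate of -8.5 or beyond has a chance of about 0.2%.
- The exchanges with the regulator are not in the documents, so -8.5 may have been a regulatory condition. That affects which rule to choose, not the need to choose one.

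**Conclusion.** The concern holds and must be fixed before unblinding. The plan contains two success rules that can disagree, and no text settles which governs. The sample size of 18 per arm is right for the zero-difference test and for nothing else stated. If -8.5 is a pass mark, power at the plan's own planning difference is 50%, not 80%. This is exact at any sample size for the point-estimate rule, given an unbiased and symmetric estimate. For the joint rule it holds at 18 per arm and above. At SD 8.9 and 18 per arm the undecided range is about -6.0 to -8.5, and 29.5% of trials would fall in it at a true -8.5. The practical loss shrinks as the true effect grows towards -13.82, but the plan claims its 80% at -8.5.

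**What to change.** State one rule, and align the hypotheses and the power statement with it.

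**Preferred.** Null: the adjusted mean difference is zero. Alternative: it is not zero. Success is a two-sided p<0.05 in favour of active from the primary ITT/LOCF ANCOVA. Describe -8.5 only as the planning difference, and report the estimate and its 95% CI against it as clinical context.

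**If -8.5 must remain a condition**, for example because it was agreed with the regulator: say that both conditions must be met and that -8.5 applies to the observed adjusted difference. Restate the power as about 50% at a true -8.5, with 80% reached at about -11.

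Either option costs SAP wording only, with no extra patients or data. Under the first, 18 evaluable per arm stays correct. Under the second, the sponsor accepts the lower stated power at -8.5, which a larger trial cannot raise.

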The CGI is rated on a 7-point scale. The clinician is asked to rate the patient relative to his or her prior experience with other patients with the same diagnosis, with or without collateral information. The CGI is a robust measure of efficacy in many clinical trials and is easy and quick to administer.

CLINICAL GLOBAL IMPRESSIONS SCALE - SEVERITY OF ILLNESS (CGI-S)

The CGI-S is an observer (clinician)-rated scale that measures illness severity.

The physician rates the patient on the CGI-S according to the following question: "Considering your total clinical experience with this patient population, how ill is the patient at this time?"

0 = Not assessed 4 = Moderately ill 1 = Normal, not at all ill 5 = Markedly ill 2 = Borderline ill 6 = Severely ill

3 = Mildly ill 7 = Among the most extremely ill patients

CLINICAL GLOBAL IMPRESSIONS SCALE - GLOBAL IMPROVEMENT (CGI-I)

The CGI-I is an observer (clinician)-rated scale that measures global improvement or change.

The physician rates the patient's condition at each applicable evaluation visit according to how much the patient's condition has changed since baseline evaluation on the following CGI-I scale. The total improvement is rated whether or not, in the physician's judgment, it is due entirely to the study intervention.

0 = Not assessed 4 = No change

1 = Very much improved 5 = Minimally worse

2 = Much improved 6 = Much worse

3 = Minimally improved 7 = Very Much Worse

References

- ✓ Leon AC, Shear MK, Klerman GL, Portera L, Rosenbaum JF, Goldenberg I. A comparison of
- ✓ symptom determinants of patient and clinician global ratings in patients with panic disorder and depression. J Clin Psychopharmacol 1993; 13(5):327–31.

The **Spanish Editions** of the CGI-S and CGI-I that will be administered in this study are the published translations for 'Spanish for Mexico' translation as per the National Institute of Mental Health (NIMH), United States Department of Health and Human Services (HHS) and distributed by:

Mapi Research Trust [name] USA www.mapi-trust.org

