A list of the following information about a subject's current and past medication and therapy use will be recorded:

- ✓ All prescription and OTC medications used to date to treat the subject's symptoms of autistic disorder. Include information on daily dosage and duration of use, as applicable:
 - Current medications
 - Non-current medications
- ✓ All therapies (conventional and alternative) used to date to treat the subject's symptoms of autistic disorder. Include information on frequency and duration of application, as applicable:
 - Current therapies
 - Non-current therapies
- ✓ All current medications (prescription and OTC) and therapies (conventional and alternative) currently used for non-autism disorder related indications. Include information on medication dosages and duration of use and frequency and duration of therapy applications, as applicable, as well as the indications for which each is being used.

BASELINE EVALUATION

The following tools from the Study Test Battery to be used during Study Baseline Assessment:

- Aberrant Behavior Checklist (ABC)
- Clinical Global Impressions (CGI) Severity of Illness Scale (CGI-S) only

PROCEDURE ADMINISTRATION PHASE

GENERAL ASSESSMENT CONDITIONS

- Subjects will be required to maintain their regular medication and dosage schedule used to treat symptoms related to autism disorder throughout the study. Subjects will not be required to stop taking any medications used to treat their autism disorder symptoms or for any other indication, as already prescribed by a treating physician, throughout the duration of participation in the study.
- Subjects must agree to not start taking any new medications, or partake in any other new non-study treatments, or to change the dosages they take of current medications, to treat the symptoms of autism disorder, during study participation.
- Subjects must agree to notify the study investigator immediately if their treating physician makes any change to medication, medication dosage or other treatment plan. The PI will evaluate the information to determine, in his or her professional opinion, if the changes are substantial enough to warrant withdrawal of the subject from further study participation.

[figure not shown]
STUDY TREATMENT ADMINISTRATION PROTOCOL

- > The study treatment administration phase will extend over four consecutive weeks.

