Therefore, the clinically significant effect size of the Erchonia® HLS Laser Device as applied to children and adolescents with autistic disorder in the proposed clinical study based on prior experience and research is defined as a minimum mean difference of -8.5 points on the ABC Irritability Subscale score from baseline to endpoint (week four) between active and placebo treatment groups.

SECONDARY EFFICACY OUTCOME MEASURES

The following secondary efficacy outcome measures will be evaluated in this study:

- ➤ Positive Response Rate: Difference in Positive Response Rate between treatment groups, where 'Positive Response Rate' is defined as satisfaction of both of the following 2 criteria:
 - ✓ >= 25% reduction from baseline to endpoint in the Aberrant Behavior Checklist (ABC) Irritability Subscale score based on the subject's primary caregiver's rating; AND
 - ✓ Clinical Global Impressions Improvement (CGI-I) scale rating of 1 or 2 (much improved or very much improved) at study endpoint as determined by the clinician's evaluation
- ➤ Mean change from baseline to endpoint in the other 4 ABC Subscale scores, based on ratings by the subject's primary caregiver:
 - ✓ Letharqy/Social Withdrawal
 - ✓ Stereotypic Behavior
 - √ Hyperactivity/Noncompliance
 - ✓ Inappropriate Speech
- ➤ Mean change from baseline to endpoint in the global ABC score
- ➤ Change in ratings on the CGI-S from baseline to study endpoint evaluation
- ➤ Change in ratings on the CGI-I from baseline to study endpoint evaluation
- Caregiver Satisfaction with Study Outcome ratings between treatment groups and across evaluations

STATISTICAL METHODS

Efficacy analysis will be according to the intent to treat (ITT) principle by last observation carried forward (LOCF).

Intent to Treat: Subjects will be included in the ITT analysis if they complete their baseline clinical assessments and had at least one post-randomization efficacy evaluation and corresponding baseline value.

Last observation carried forward (LOCF): Missing data will be handled by carrying forward the last observation for the relevant measure. The LOCF data set included date recorded at a given time point, or, if no observation was recorded at that time point, data carried forward from the previous time point with available data. Baseline data will not be carried forward or averaged to impute missing values for the LOCF data set.

STATISTICAL ANALYSIS

Primary Efficacy Analysis

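### The CGI-I secondary outcome asks for change from a baseline rating that cannot exist, and the CGI test is named without its statistic, scores or strata

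*Combined protocol and SAP*

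**What the plan says.** All places are in the combined protocol and SAP.

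- **Secondary Efficacy Outcome Measures** lists two CGI outcomes in parallel wording: "Change in ratings on the CGI-S from baseline to study endpoint evaluation" and "Change in ratings on the CGI-I from baseline to study endpoint evaluation". In the same list, the responder definition uses the CGI-I differently, as a "scale rating of 1 or 2 (much improved or very much improved) at study endpoint as determined by the clinician's evaluation".
- **Clinical Global Impressions Scale - Global Improvement (CGI-I)** has the physician rate the child at each applicable visit "according to how much the patient's condition has changed since baseline evaluation on the following CGI-I scale". A rating of 4 means no change.
- **Baseline Evaluation** restricts the CGI at that visit to "Clinical Global Impressions (CGI) Severity of Illness Scale (CGI-S) only". Under Study Evaluation Timeline, the CGI is then recorded at Weeks 2, 4 and 8.
- **Statistical Methods** defines the ITT set as children who complete baseline assessments and "had at least one post-randomization efficacy evaluation and corresponding baseline value".
- **Secondary Measures Analysis** gives one sentence for the CGI: "The categorical measures of the CGI will be analyzed within the framework of the generalized Cochran-Mantel Haenszel (CMH) procedure". For the other ABC subscales and the global score it is specific: "The ANCOVA models for LOCF data sets will include the baseline measure as a covariate".

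**The concern.** There are two separate problems.

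First, the CGI-I outcome has no baseline term. An analyst following the text could use the Week 4 rating, subtract the Week 2 rating from the Week 4 rating, or assign everyone a baseline of 4. The second of these measures something else, namely movement during the last two weeks of treatment. The ITT condition makes matters worse if it is applied measure by measure.

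Second, generalized CMH is a family of tests. It includes a general-association statistic that ignores the order of the ratings, a row-mean-scores statistic and a correlation statistic, each with or without strata. The plan does not choose among them, and does not say whether the response is the Week 4 category or the change. With 20 children per arm these choices can differ considerably in power. A choice made after unblinding would leave the clinician-rated results open to a charge of selection, in data intended for a de novo application.

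**Working it through.** **The plan's own figure.** The documents give no power or sample size for any CGI outcome. The stated size belongs to the primary endpoint and reproduces: n per arm = 2 × (1.960 + 0.842)² × (8.9/8.5)² = 17.2, rounded up to 18, which the plan then inflates to 20. Nothing below alters it.

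**CGI-I, by tracing the text.**
1. Each CGI-I rating is defined as change since baseline, so a rating at baseline has no meaning.
2. The baseline visit collects CGI-S only, so the number of baseline CGI-I ratings is 0.
3. A literal difference, Week 4 CGI-I minus baseline CGI-I, therefore cannot be formed for any child.
4. A literal reading of the ITT condition, applied to the CGI-I, leaves 0 evaluable children.
5. The Week 4 CGI-I rating exists and already expresses change from baseline. The responder definition uses it that way.

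**CGI-S, by tracing the text.** The CGI-S is rated at baseline and the CGI is recorded at Week 4, so the change can be computed and a CMH test applied. What is missing is the response variable, the scores, the statistic and the strata.

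**Why the missing details matter.** Take the endpoint variance as 1, with equal variances at both visits and baseline-to-endpoint correlation ρ. An unadjusted change score has variance 2(1 − ρ). A baseline-adjusted endpoint has variance 1 − ρ².

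| ρ | Change, 2(1 − ρ) | Adjusted, 1 − ρ² |
|---|---|---|
| 0.3 | 1.40 | 0.91 |
| 0.5 | 1.00 | 0.75 |
| 0.7 | 0.60 | 0.51 |

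Adjustment helps most when the correlation is low, and the two converge as it rises.

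**Simulated power for the CGI-S.** These inputs are assumptions and are not in the documents: 20 per arm, latent SD 0.9, baseline ratings 4 to 7, a 0.8-point treatment effect, and a two-sided 5% test.

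| Test | ρ = 0.3 | ρ = 0.5 | ρ = 0.7 |
|---|---|---|---|
| General association on change | 21% | 34% | 57% |
| Row-mean-scores on change | 58% | 68% | 86% |
| Row-mean-scores on Week 4 rating, stratified by baseline CGI-S | 70% | 77% | 87% |

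Type I error is about 5% or lower for all three. With 18 per arm the pattern is the same: 18-52%, 52-82% and 65-83% respectively.

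An ordered statistic on change gains 58 − 21 = 37, 68 − 34 = 34 and 86 − 57 = 29 points over general association. Stratifying by baseline adds a further 70 − 58 = 12, 77 − 68 = 9 and 87 − 86 = 1 points.

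**The case against.** The strongest reply is that the CGI-I problem is one of wording and that context largely settles it. The scale definition makes the Week 4 rating the change from baseline, and the responder definition uses it directly. Setting every child's baseline to 4 would subtract a constant and leave a between-group CMH comparison unchanged. This stands as an argument that the repair is easy. It does not make the sentence correct, and it does not dispose of the ITT condition.

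A reader might go further and infer that neither CGI outcome can be run, or that the CGI-S analysis ignores baseline. The documents support neither. The CGI-S change is computable from collected data, a change score uses the baseline, and generalized CMH can be stratified by it. The plan is silent on strata; it does not rule them out. Nor does it name general association, so the low power figures describe a permitted choice and not a stated one.

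The power figures also depend on the assumed effect. At a 1.6-point effect, with the same SD and correlations, both ordered tests reach about 99-100% and general association 84-100%. The prior study reported a large CGI-S difference at Week 8 (100% of placebo against 35% of active subjects still rated 5 to 7). However, its active figure pools randomized and crossover subjects and is not a safe planning value.

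Finally, study success rests on ABC Irritability, and no power claim or success criterion attaches to the CGI. That limits the importance of the point without removing it.

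**Conclusion.** The point holds in two parts. The CGI-I outcome is wrong as written: it requires a baseline rating that is not collected and by definition cannot be. That follows from the text alone and needs no assumption. The CGI-S outcome can be run but is under-specified, with no stated statistic, scores, strata or baseline adjustment, whereas the ABC models do state theirs.

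The size of the second part is illustrative and rests on the assumed SD, effect and correlations. Most of the possible loss, roughly 30 to 37 points of power, comes from whether the test uses the order of the ratings. Stratifying by baseline is worth about 12 points at a correlation of 0.3 and close to nothing at 0.7. Precision and prespecification are at stake, not type I error. Only secondary outcomes are affected; the primary ABC Irritability analysis and the responder analysis stand as they are. The correction should be made before unblinding.

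**What to change.** - **Secondary Efficacy Outcome Measures:** replace the CGI-I change outcome with the CGI-I rating at Week 4, compared between treatment groups.
- **Statistical Methods, ITT definition:** add that the baseline-value condition does not require a baseline CGI-I.
- **Secondary Measures Analysis:** state that the Week 4 CGI-S and Week 4 CGI-I ratings are each compared by the row-mean-scores CMH test with midrank scores, stratified by baseline CGI-S. Other ordered, baseline-adjusted tests would also be reasonable; what matters is that one is named in advance.

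The cost is about three sentences. The change uses ratings already scheduled and adds no visit, assessment or child.
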